1.3 Schema

The general study design is summarized in [Figure 1](#).

Figure 1 Study design

BED = bioequivalent dose; DoR = Duration of response; Durva = durvalumab; ECOG = Eastern Cooperative Oncology Group; Gy = gray; m = Month; mOS = median overall survival; mPFS = median progression-free survival; NSCLC = Non-small cell lung cancer; ORR = Overall response rate; OS12 = Overall survival at 12 months; PD = Progressive disease; PFS6, PFS12 = Progression-free survival at 6, 12 months, respectively; PRAE = Possibly related adverse event; PS = Performance status; q4w = Every 4 weeks; RT = radiation therapy

2 INTRODUCTION

Lung cancer has been the most common cancer in the world for several decades, and by 2012, there were an estimated 1.8 million new cases, representing 12.9% of all new cancers. It was also the most common cause of death from cancer, with 1.59 million deaths (19.4% of the total)

(GLOBOCAN 2012). NSCLC represents approximately 80% to 85% of all lung cancers and 30% of patients present with Stage III disease. Standard treatment for patients with a good performance status (PS) and unresectable Stage III NSCLC had been platinum-based doublet chemotherapy and radiotherapy administered concurrently with cCRT. A meta-analysis of concurrent versus sequential CRT demonstrated better outcomes with concurrent therapy, but even with cCRT, 5-year OS ranges between 15% and 32% (Antonia et al 2017, Aupérin et al 2010).

More recently, the PACIFIC Study (D4191C00001) demonstrated that the addition of durvalumab as sequential therapy to platinum-based CRT significantly improves PFS (median PFS 17.2 months with durvalumab compared to 5.6 months with placebo, hazard ratio [HR] of 0.51) and OS (HR of 0.68) (Antonia et al 2018). Given the potential for further clinical benefit, the Sponsor is currently evaluating the efficacy and safety of durvalumab given concurrently with platinum-based CRT in patients with locally-advanced, unresectable NSCLC (Stage III) in PACIFIC2 (D933KC00001).

However, a significant proportion of patients with Stage III unresectable NSCLC are ineligible for chemotherapy for a number of reasons, including comorbidities, poor PS, or elderly age; these patients are therefore faced with fewer treatment options. A common regimen for these patients is radiotherapy alone; however, it is associated with disappointing results in terms of OS (Driessen et al 2016; Miller et al 2018). Using durvalumab subsequent to radiation therapy could potentially provide better clinical outcomes in this population.

2.1 Study rationale

Over the last decade, there has been an increasing interest in studying the therapeutic potential of immune therapy for different types of tumors. In particular, nonclinical and clinical studies have indicated that blockade of immune checkpoints can have a positive effect on antitumor immunity.

Results of early studies with durvalumab in advanced cancers are consistent with a class effect of early and sustained tumor control that has been observed previously with other inhibitors of the immune-checkpoint pathway. A consistent observation across these studies is the long durability of benefits with immune-checkpoint inhibitors. However, not all patients benefit from immune-checkpoint inhibitors as monotherapy. Hence, studies that follow established treatments (such as radiation therapy) with immune-checkpoint inhibitors are needed in order to expand the patient population who might benefit from immune-checkpoint inhibitors.

Radiation has been shown to induce immunogenic cell death. Cell death enhances the ability of the immune system to recognize and respond to the tumor through enhanced antigen release and presentation (tumor specific T-cell activation; Formenti and Demaria 2013, Weichselbaum et al 2017). In addition, ionizing radiation causes upregulation of various proinflammatory

signals and cytokines, which play a key role in immune regulatory pathway, leading to improved antitumor immunity. Twyman-Saint Victor et al also showed that radiation enhanced the diversity of the T-cell receptor repertoire of intratumoral T cells (Twyman-Saint Victor et al 2015). Additionally, radiotherapy has been shown to upregulate the expression of PD-L1 (Butts et al 2014, Deng et al 2014, Zhang et al 2008b), and therefore may confer greater sensitivity to PD-L1-directed therapy.

2.2 Background

A detailed description of the chemistry, pharmacology, efficacy, and safety of durvalumab is provided in the IB.

2.2.1 Immunotherapies

It is increasingly understood that cancers are recognized by the immune system, and under some circumstances, the immune system may control or even eliminate tumors (Dunn et al 2004).

PD-L1 is part of a complex system of receptors and ligands that are involved in controlling T-cell activation. The PD-1 receptor (CD279) is expressed on the surface of activated T cells (Janssen et al 2008a, Janssen et al 2008b, Keir et al 2008). It has 2 known ligands: PD-L1 (B7-H1; CD274) and PD-L2 (B7-DC; CD273) (Okazaki and Honjo 2007). PD-1 and PD-L1/PD-L2 belong to a family of immune-checkpoint proteins that act as co-inhibitory factors, which can halt or limit the development of T-cell response. When PD-L1 binds to PD-1, an inhibitory signal is transmitted into the T cell, which reduces cytokine production and suppresses T-cell proliferation. Tumor cells exploit this immune checkpoint pathway as a mechanism to evade detection and inhibit immune response.

PD-L1 is constitutively expressed by B-cells, dendritic cells, and macrophages (Qin et al 2016). Importantly, PD-L1 is commonly over-expressed on tumor cells or on non-transformed cells in the tumor microenvironment (Pazdur 2008, Pardoll 2012). PD-L1 expressed on the tumor cells binds to PD-1 receptors on the activated T cells, leading to the inhibition of cytotoxic T cells. These deactivated T cells remain inhibited in the tumor microenvironment. The PD-1/PD-L1 pathway represents an adaptive immune resistance mechanism that is exerted by tumor cells in response to endogenous antitumor activity.

The inhibitory mechanism described above is co-opted by tumors that express PD-L1 as a way of evading immune detection and elimination. The binding of an anti-PD-L1 agent to the PD-L1 receptor inhibits the interaction of PD-L1 with the PD-1 and CD80 receptors expressed on immune cells. This activity overcomes PD-L1-mediated inhibition of antitumor immunity. While functional blockade of PD-L1 results in T-cell reactivation, this mechanism of action is different from direct agonism of a stimulatory receptor such as CD28.

PD-L1 is expressed in a broad range of cancers. Based on these findings, an anti-PD-L1 antibody could be used therapeutically to enhance antitumor immune responses in patients with cancer. Results of nonclinical and clinical studies of mAbs targeting the PD-L1/PD-1 pathway have shown evidence of clinical activity and a manageable safety profile, supporting the hypothesis that an anti-PD-L1 antibody could be used to therapeutically enhance antitumor immune response in cancer patients (Antonia et al 2017, Antonia et al 2018, ASTRO 2017, Aupérin et al 2010, Basch et al 2009, Bergman et al 1994, Herdman et al 2011, Hirano et al 2005, IASLC 2016, Iwai et al 2002, Okudaira et al 2009, Topalian et al 2012, Zhang et al 2008a) with responses that tend to be more pronounced in patients with tumors that express PD-L1 (Pickard et al 2007, Powles et al 2014, Rizvi et al 2015, Segal et al 2015). In addition high mutational burden (eg, in bladder carcinoma; Aaronson et al 1993, Alexandrov et al 2013) may contribute to the responses seen with immune therapy.

Nonclinical data have now been added to a wealth of clinical data showing that blockade of negative regulatory signals to T cells such as cytotoxic T-lymphocyte-associated antigen-4 (CTLA-4) and PD-L1 has promising clinical activity. Ipilimumab was first granted United States Food and Drug Administration approval for the treatment of metastatic melanoma and is currently under investigation for several other malignancies. Nivolumab and pembrolizumab, 2 anti-PD-1 agents, and atezolizumab, an anti-PD-L1 agent, have been granted approvals by agencies for the treatment of a number of malignancies including metastatic melanoma, squamous and nonsquamous cell NSCLC, squamous cell carcinoma of the head and neck, and urothelial carcinoma. In addition, there are data from agents in the anti-PD-1/PD-L1 class showing clinical activity in a wide range of tumor types.

2.2.2 Durvalumab

Durvalumab is a human mAb of the IgG1 kappa subclass that blocks the interaction of PD-L1 (but not programmed cell death ligand-2) with PD-1 on T cells and CD80 (B7.1) on immune cells. It is being developed by AstraZeneca/MedImmune for use in the treatment of cancer. (MedImmune is a wholly owned subsidiary of AstraZeneca; AstraZeneca/MedImmune will be referred to as AstraZeneca throughout this document.) The proposed mechanism of action (MOA) for durvalumab is interference in the interaction of PD-L1 with PD-1 and CD80 (B7.1). Blockade of PD-L1/PD-1 and PD-L1/CD80 interactions releases the inhibition of immune responses, including those that may result in tumor elimination. In vitro studies demonstrate that durvalumab antagonizes the inhibitory effect of PD-L1 on primary human T cells resulting in the restored proliferation of interferon gamma (IFN- γ) (Sprangers and Aaronson 1992, Stewart et al 2015). In vivo studies have shown that durvalumab inhibits tumor growth in xenograft models via a T-cell-dependent mechanism (Sprangers and Aaronson 1992, Stewart et al 2015). Based on these data, durvalumab is expected to stimulate the patient's antitumor immune response by binding to PD-L1 and shifting the balance toward an antitumor response. Durvalumab has been engineered to reduce antibody-dependent cellular cytotoxicity and complement-dependent cytotoxicity.

To date, durvalumab has been given to more than 5000 patients as part of ongoing studies either as monotherapy or in combination with other anticancer agents. Details on the safety profile of durvalumab monotherapy are summarized in Section 4.3.1 and Section 8.3.12. Refer to the current durvalumab IB for a complete summary of nonclinical and clinical information including safety, efficacy, and pharmacokinetics (PK).

2.3 Benefit/risk assessment

The majority of the safety and efficacy data currently available for durvalumab are based on the first-in-human, single-agent study (Study CD-ON-MEDI4736-1108; hereafter referred to as Study 1108) in patients with advanced solid tumors, the study of durvalumab monotherapy in NSCLC (ATLANTIC Study [NCT02087423]), the study of durvalumab monotherapy in NSCLC following completion of platinum-based chemotherapy concurrent with radiation therapy (PACIFIC Study [NCT02125461]), and the study of durvalumab with or without tremelimumab as first line treatment for patients with advanced or metastatic NSCLC (MYSTIC Study [NCT02453282]). Data from these studies have demonstrated clinical activity of durvalumab therapy in patients with NSCLC. Details pertaining these studies are provided in the current durvalumab IB.

More detailed information about the known and expected benefits and risks and reasonably expected AEs of durvalumab may also be found in the IB.

2.3.1 Potential benefits

The efficacy of durvalumab was evaluated in the Phase III PACIFIC Study, a multi-center, randomized, double-blind, placebo-controlled study in patients with unresectable Stage III NSCLC who completed at least 2 cycles of concurrent platinum-based chemotherapy and definitive radiation within 42 days prior to initiation of the study drug and had a World Health Organization (WHO) PS 0 or 1 ([Antonia et al 2017](#), [Antonia et al 2018](#)). A total of 713 patients were randomized 2:1 to receive durvalumab 10 mg/kg or placebo intravenously every 2 weeks for up to 12 months or until unacceptable toxicity or confirmed RECIST 1.1-defined progression. The prespecified interim PFS analysis based on 81% of total planned events demonstrated a statistically significant improvement in PFS of 16.8 months (95% CI: 13.0, 18.1) with durvalumab versus 5.6 months (95% CI: 4.6, 7.8) with placebo (stratified HR: 0.52; 95% CI: 0.42, 0.65; $p < 0.001$). The PFS benefit in favor of durvalumab was observed irrespective of PD-L1 expression before CRT (PD-L1 expression $< 25\%$, HR: 0.59; 95% CI: 0.43, 0.82; PD-L1 expression $\geq 25\%$, HR: 0.41; 95% CI: 0.26, 0.65). The response rate was higher with durvalumab than with placebo (28.4% versus 16.0%; $p < 0.001$), and the median duration of response (DoR) was longer (72.8% versus 46.8% of the patients had an ongoing response at 18 months).

As of the time of the PACIFIC OS analysis, the median time to death or distant metastasis was 28.3 months in the durvalumab group and 16.2 months in the placebo group (stratified HR, 0.53;

95% CI, 0.41 to 0.68) ([Antonia et al 2018](#)). The 24-month OS rate was 66.3% (95% CI, 61.7 to 70.4) in the durvalumab group, as compared with 55.6% (95% CI, 48.9 to 61.8) in the placebo group (two-sided P 0.005). As of 31 January 2019 (third data cutoff [DCO]), 3-year data demonstrated a durvalumab survival benefit over placebo that was consistent with the OS primary analysis, with a 31% reduction in the risk of death (HR: 0.69; 95% CI, 0.55 to 0.86). The Kaplan-Meier estimate of the median OS was 29.1 months in the placebo group, while it was not yet reached in the durvalumab group. The 12-, 24-, and 36-month OS rates with durvalumab and placebo were 83.1% versus 74.6%, 66.3% versus 55.3%, and 57.0% versus 43.5%, respectively ([Gray et al 2019](#)).

2.3.2 Overall risks

Monoclonal antibodies directed against immune-checkpoint proteins, such as PD-L1 as well as those directed against PD-1 or CTLA-4, aim to boost endogenous immune responses directed against tumor cells. By stimulating the immune system, however, there is the potential for adverse effects on normal tissues.

Most adverse drug reactions seen with the immune-checkpoint inhibitor class of agents are thought to be due to the effects of inflammatory cells on specific tissues. These risks are generally events with a potential inflammatory or immune-mediated mechanism and that may require more frequent monitoring and/or unique interventions such as immunosuppressants and/or endocrine therapy. These immune-mediated effects can occur in nearly any organ system, and are most commonly seen as gastrointestinal AEs such as colitis and diarrhea, pneumonitis/interstitial lung disease (ILD), hepatic AEs such as liver enzyme elevations, skin events such as rash and dermatitis, and endocrinopathies including hypo- and hyper-thyroidism.

2.3.2.1 Durvalumab

Risks with durvalumab include, but are not limited to, diarrhea/colitis, pneumonitis/ILD, endocrinopathies (ie, events of hypophysitis/hypopituitarism, adrenal insufficiency, hyper- and hypothyroidism, type I diabetes mellitus, and diabetes insipidus), hepatitis/increases in transaminases, nephritis/increases in creatinine, pancreatitis/increases in amylase and lipase, rash/dermatitis, myocarditis, myositis/polymyositis, infusion-related reactions, hypersensitivity reactions, pancreatitis, serious infections, and other rare or less frequent inflammatory events including neuromuscular toxicities (eg, Guillain-Barre syndrome, myasthenia gravis).

For information on all identified and potential risks with durvalumab, please always refer to the current version of the durvalumab IB.

In monotherapy clinical studies, AEs at an incidence of > 20% include events such as fatigue, cough, decreased appetite, dyspnea, and nausea. Approximately 10% of patients discontinued the drug due to an AE. In the PACIFIC Study in patients with Stage III NSCLC following cCRT, AEs (all causality) experienced during the study with an incidence of > 10% (durvalumab vs

placebo) were cough (35.4% vs 25.2%); fatigue (23.8% vs 20.5%); dyspnea (22.3% vs 23.9%); radiation pneumonitis (20.2% vs 15.4%); diarrhea (18.3% vs 18.8%); pyrexia (14.7% vs 9%); decreased appetite (14.3% vs 12.8%); nausea (13.9% vs 13.2%); pneumonia (13.1% vs 7.7%); pneumonitis (12.6% vs 7.7%); arthralgia (12.4% vs 11.1%); pruritus, rash and upper respiratory tract infection (12.2% each vs 4.7%, 7.3% and 9.8%, respectively); constipation (11.8% vs 8.5%); hypothyroidism (11.6% vs 1.7%); headache (10.9% vs 9.0%); asthenia (10.7% vs 13.2%); and back pain (10.5% vs 11.5%). Combined events of pneumonitis or radiation pneumonitis occurred in 33.9% vs 24.8% of patients, including CTCAE Grade 3 pneumonitis or radiation pneumonitis in 3.4% vs 2.6% of patients; no patients in either treatment group reported Grade 4 events of pneumonitis or radiation pneumonitis.

Please see the current version of the IB for a detailed summary of the monotherapy data including AEs, serious adverse events (SAEs), and CTCAE Grade 3 to 5 events reported across the durvalumab program.

The majority of treatment-related AEs were manageable with dose delays, symptomatic treatment, and in the case of events suspected to have an immune basis, the use of established treatment guidelines for immune-mediated toxicity (see Section 8.4.5).

A detailed summary of durvalumab monotherapy AE data can be found in the current version of the durvalumab IB.

2.3.3 Overall benefit/risk

The clinical activity associated with potentiating the proinflammatory effects of radiation therapy suggests that giving durvalumab following radiation therapy may have clinical benefits, including increasing the response rate to radiation therapy.

The safety of durvalumab following radiation therapy is further supported by results from the PACIFIC Study, which showed that durvalumab administered within 42 days of completion of CRT had a well tolerated and manageable safety profile that was consistent with the established safety profile to date. It is therefore reasonable to assume that immunotherapy administered within 42 days of completion of radiation therapy will also be well tolerated.

Therefore, the overall benefit-risk assessment supports the proposed study to evaluate the efficacy and safety of administration of durvalumab following radiation therapy.

3 OBJECTIVES AND ENDPOINTS

The study objectives and corresponding endpoints/variables are listed in Table 3.

Table 3 Study objectives and endpoints

AE = Adverse event; AESI = Adverse event of special interest; BP = blood pressure; DoR = Duration of response;

AE = Adverse event; AEsI = Adverse event of special interest; CTCAE = Common Terminology Criteria for Adverse Event; CCI = Clinical Impression.

ECG = Electrocardiogram; CCI

CCI

CCI

imAE = Immune-mediated adverse events; IP = Investigational product; NCI = National Cancer Institute; ORR = Objective response rate; OS = Overall survival; OS12 = Proportion of patients alive at 12 months from first date of treatment; CCI ; PFS = Progression-free survival; PFS6, PFS12 = Progression-free survival at 6, 12 months, respectively; CCI ;

CCI

PRAE = Possibly related adverse event;

CCI

RECIST 1.1 = Response Evaluation Criteria in Solid Tumors version 1.1; SAE = Serious adverse event; TL = Target lesion; CCI .

Note: Toxicities will be classified as per CTCAE grading system NCI CTCAE version 5.0. Analysis of ORR and DoR will be based upon Investigator assessment according to RECIST 1.1. Prior irradiated lesions may be considered measurable and selected as TLs providing they fulfill the other criteria for measurability.

Note: An AESI is an AE of scientific and medical interest specific to understanding of the IP. AESIs for durvalumab include, but are not limited to, events with a potential inflammatory or immune-mediated mechanism and which may require more frequent monitoring and/or interventions such as steroids, immunosuppressants, and/or hormone replacement therapy. Please refer to Section [8.3.12](#) for AESI definition.

4 STUDY DESIGN

4.1 Overall design

This is a Phase II open-label, single-arm, multicenter, international study to evaluate the clinical activity of durvalumab (1500 mg q4w) in patients with Stage III unresectable NSCLC who have an Eastern Cooperative Oncology Group (ECOG) PS of 0 to 2 and who were treated with radiotherapy but are ineligible for chemotherapy. Patients will be enrolled into 2 cohorts according to the dose of radiotherapy received prior to study entry (Cohort A: Standard Radiotherapy [60 Gy \pm 10% or hypofractionated BED]; Cohort B: Palliative Radiotherapy [40 to < 54 Gy or hypofractionated BED]).

Approximately 150 patients will be treated with the study drug in Europe and North America. Patients will be in CR, PR, or have SD following radiation therapy, as assessed by the Investigator and further supported by the screening imaging radiological assessment. Patients must not have progressed following radiation therapy, and radiation therapy must be completed within 6 weeks (42 days) prior to first IP dose administration. The last dose of radiation therapy is defined as the day of the last radiation treatment session.

Patients must have histologically- or cytologically-documented NSCLC and locally-advanced, unresectable Stage III disease (according to the International Association for the Study of Lung Cancer [IASLC] Staging Manual Version 8 [\[IASLC 2016\]](#)). Patients must be deemed to be ineligible for chemotherapy per Investigator assessment.

For an overview of the study design see [Figure 1](#), Section [1.3](#). For details on treatments given during the study, see Section [6.1](#) Treatments Administered.

For details on what is included in the efficacy and safety endpoints, see Section 3 Objectives and Endpoints.

Patients will receive study treatment for 12 months or until RECIST 1.1-defined radiological progression by Investigator unless there is evidence of an unacceptable toxicity, or if the patient requests to stop the study treatment. See Section 6.1.3 for detailed criteria.

Patients who have discontinued study treatment due to toxicity or symptomatic deterioration, clinical progression, or who have commenced subsequent anticancer therapy, will be followed up for AEs and with PRO-questionnaires for 90 days after study treatment discontinuation, and thereafter followed up with tumor assessments until RECIST 1.1-defined radiological PD plus an additional follow-up scan or until death (whichever comes first).

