Section Number and Name	Description of Change	Brief Rationale	Substantial or Non-substantial
Section 4.1 Overall design; Table 2, footnotes; Section 7.1.1 Follow-up of patients post- discontinuation of study treatment; Section 7.1.2 Follow-up for survival	The minimum expected safety follow-up period of 90 days following the last dose of durvalumab for patients treated with the study treatment has been detailed and clarified, and accordingly new sections (Section 7.1.1 and 7.1.2) were added.	Text related to follow-up of patients after discontinuation of study treatment has been clarified.	Non-substantial
Section 4.4; Section 6.1.3 Duration of treatment and criteria for treatment through progression	A new section as “Continued access to study treatment” was added.	To clarify initial intent to allow continuation of the treatment with durvalumab for patients who may benefit from it, based on investigator’s opinion, after the individual patient reached end of scheduled visits, but before the study reached last patient last visit/final DCO date.	Non-substantial
Synopsis; Section 1.3 Schema; Section 9.2 Sample size estimate	Details related to sample size update were included.	To aid patient recruitment, details about the adequate sample size were included.	Non-substantial
Section 9.5 Statistical analysis	Details related to data analysis (DCO for the primary analysis) were added.	To aid patient recruitment, details were included.	Non-substantial
Section 4.4	Clarified definition of the end of study according to European Union and Food and Drug Administration requirements.	For consistency and alignment in terms of posting study results.	Non-substantial

Section Number and Name	Description of Change	Brief Rationale	Substantial or Non-substantial
Section 6	Updated the definition for “study treatments” and details of durvalumab in Table 5. Also updated text describing administration of study treatment.	For consistency and alignment with regulatory requirements.	Non-substantial
Section 8.4.1	Updated text pertaining to reporting of SAEs when EDC system is not available/temporarily not accessible. Also specified the reference document for definition of expectedness/listedness.	Updated to comply with regulatory requirements.	Non-substantial
Section 8.4.3	Specified timelines for providing relevant information to the AstraZeneca Patient Safety data entry site.	Updated to comply with regulatory requirements.	Non-substantial

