Patients will be enrolled into 2 cohorts according to radiotherapy pretreatment dose (Cohort A: standard radiation therapy [60 gray (Gy) \pm 10% or hypofractionated bioequivalent dose (BED)]; Cohort B: palliative radiation therapy [40 to < 54 Gy or hypofractionated BED]). This study will be conducted in Europe and North America.

Study period

Estimated date of first patient enrolled: Q2 2020

Estimated date of last patient completed: Q2 2023

Number of patients

Approximately 102 patients are being treated with durvalumab in this study in Europe and North America. Patients will be in complete response (CR), partial response (PR), or have stable disease (SD) following radiation therapy, as assessed by the Investigator and further supported by the screening imaging radiological assessment. Patients must not have progressed following

radiation therapy, and radiation therapy must be completed within 6 weeks (42 days) prior to first durvalumab administration. The last dose of radiation therapy is defined as the day of the last radiation treatment session.

Approximately 148 patients are screened to achieve 102 patients treated with durvalumab and 60 evaluable patients.

Note: "Screened" means a patient's or their legally acceptable representative's, agreement to participate in a clinical study following completion of the informed consent process. Potential patients who are screened for the purpose of determining eligibility for the study, but are not randomized/assigned in the study, are considered "screen failures", unless otherwise specified by the protocol.

Treatments and treatment duration

All patients will receive 1500 mg durvalumab via intravenous (IV) infusion every 4 weeks (q4w) for 12 months (13 doses/cycles). The last administration of durvalumab will be on week 48 unless there is clinical progression, confirmed radiological progression, unacceptable toxicity, withdrawal of consent, or another discontinuation criterion is met. (Please note: If a patient's weight falls to 30 kg or below, the patient should receive weight-based dosing equivalent to 20 mg/kg of durvalumab q4w after consultation between Investigator and Study Physician, until the weight improves to > 30 kg, at which point the patient should resume the fixed-dosing of durvalumab 1500 mg q4w).

Progression during treatment

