The primary objective of this study is to assess the safety and tolerability of durvalumab which is defined as Grade 3 and Grade 4 possibly related adverse events (PRAEs), as assessed by the Investigator, observed within 6 months after the initiation of durvalumab treatment. In addition, safety and tolerability of durvalumab will be characterized for the cohorts of patients who received Standard Radiotherapy (60 Gy \pm 10% or hypofractionated BED) and patients who received palliative radiotherapy (40 to < 54 Gy or hypofractionated BED).

Safety data will be summarized descriptively overall, by seriousness, by causality and by maximum National Cancer Institute (NCI) Common Terminology Criteria for Adverse Events (CTCAE) Grade. The exact 95% confidence intervals (CIs) around the incidence of Grade 3 and Grade 4 PRAEs will be reported for patients overall and separately for each cohort.

The median PFS, median OS, and median time to NSCLC-related death, together with their corresponding 95% CIs, will be calculated using Kaplan-Meier product limit methods. The proportion of patients who are progression-free at 6 and 12 months and the proportion of patients who are alive at 12 months will be presented. In addition, the objective response rate (ORR), based on Investigator assessments, together with the corresponding 95% CIs will be reported.

[figure not shown]
A total of approximately 102 patients are treated with the study drug in 2 cohorts: approximately 59 patients in the Standard Radiotherapy Cohort and approximately 43 patients in the Palliative Radiotherapy Cohort. It is estimated that a sample size of a minimum 60 patients would be required to provide an adequate level of confidence in the estimated incidence of Grade 3 and 4

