9.2 Sample size estimate

The primary objective of this study is to assess the safety and tolerability of durvalumab which is defined as Grade 3 and Grade 4 PRAEs observed within 6 months after the initiation of durvalumab treatment. In addition, safety and tolerability of durvalumab will be characterized for the cohorts of patients who received Standard Radiotherapy (60 Gy \pm 10%) or hypofractionated BED and patients who received palliative radiotherapy (40 to < 54 Gy) or hypofractionated BED.

A total of approximately 102 patients are treated with durvalumab in 2 cohorts: approximately 59 patients in the Standard Radiotherapy Cohort and approximately 43 patients in the Palliative Radiotherapy Cohort. It is estimated that a sample size of a minimum 60 patients would be required to provide an adequate level of confidence in the estimated incidence of Grade 3 and 4 PRAEs occurring within 6 months after initiation of durvalumab treatment, which is the primary endpoint. With a sample size of 60 patients, the exact binomial 95% CI for an observed incidence rate of 12% would be 5% to 23%. If the underlying/true incidence rate was 12% as reported in PACIFIC (D4194C00006), on repeated implementations of this study, observing an incidence rate less than 5% or greater than 18.3% would be approximately 5% for each region/tail.

Furthermore, if there are 30 patients in each cohort (Standard Radiotherapy and Palliative Radiotherapy) and the true incidence of Grade 3 and Grade 4 PRAEs occurring within 6 months after initiation of durvalumab treatment is 12%, the precision will be approximately \pm 13.0% (95% CI: 3.1, 29.1) in each cohort.

An illustration of the precision around the varying incidence rate of Grade 3 and Grade 4 PRAEs for the patients overall and for each cohort (Standard Radiotherapy and Palliative Radiotherapy) is provided in [Table 11](#).

Table 11 Precision around varying incidence of Grade 3 and Grade 4 Possibly-Related Adverse Events

Sample size	Grade 3 and Grade 4 PRAE Incidence Rate		
	10 %	12 %	15 %
60	3.8-20.5 (\pm 8.4)	5.0-23.0 (\pm 9.0)	7.1-26.6 (\pm 9.7)
30	2.1-26.5 (\pm 12.2)	3.1-29.1 (\pm 13.0)	4.7-32.7 (\pm 14.0)

AE = adverse event; CI = confidence interval; n = number of patients; PRAE = possibly related adverse event; RT = radiation therapy.

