### Figure 1 Study Design

BED = bioequivalent dose; DoR = Duration of response; ECOG = Eastern Cooperative Oncology Group; Gy = gray; m = Month; mOS = median overall survival; mPFS = median progression-free survival; NSCLC = Non-small cell lung cancer; ORR = Overall response rate; OS12 = Overall survival at 12 months; PD = Progressive disease; PFS6, PFS12 = Progression-free survival at 6, 12 months, respectively; PRAE = Possibly related adverse event; PS = Performance status; q4w = Every 4 weeks; RT = radiation therapy

Approximately 102 patients will be treated with durvalumab in Europe and North America. Patients will be in complete response (CR), partial response (PR), or have stable disease (SD) following radiation therapy, as assessed by the Investigator and further supported by the screening imaging radiological assessment. Patients must not have progressed following radiation therapy, and radiation therapy must be completed within 6 weeks (42 days) prior to first durvalumab administration. The last dose of radiation therapy is defined as the day of the last radiation treatment session.

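### Protocol Section 4.1 gives about 150 treated patients, while the synopsis, Section 9.2 and the SAP give about 102

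*Protocol*

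**What the plan says.** Protocol Section 4.1 (Overall design) states: "Approximately 150 patients will be treated with the study drug in Europe and North America".

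Elsewhere the treated total is different:

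- Protocol synopsis, Number of patients: "Approximately 102 patients are being treated with durvalumab in this study in Europe and North America". The same part of the synopsis gives the screening plan: "Approximately 148 patients are screened to achieve 102 patients treated with durvalumab", with 60 of them evaluable.
- Protocol synopsis, Statistical methods: "A total of approximately 102 patients are treated with the study drug in 2 cohorts: approximately 59 patients in the Standard Radiotherapy Cohort", followed by about 43 in the palliative cohort.
- Protocol Section 9.2 (Sample size estimate): "A total of approximately 102 patients are treated with durvalumab in 2 cohorts", with the same split of 59 and 43.
- SAP Section 1.2, under Figure 1: "Approximately 102 patients will be treated with durvalumab in Europe and North America".
- SAP Section 1.3 repeats the total of 102 and the split of 59 and 43.

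The protocol's version history records a sample-size update against "Synopsis; Section 1.3 Schema; Section 9.2 Sample size estimate". Section 4.1 appears there in a different row, which concerns post-treatment follow-up: "Section 4.1 Overall design; Table 2, footnotes".

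**The concern.** Section 4.1 is where a site, an ethics committee or a regulator looks for the size and shape of the study. It gives a treated population nearly half as large again as the one in the synopsis, the sample-size section and the SAP.

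The figures count the same thing. The sentences in Section 4.1, the synopsis and SAP Section 1.2 all concern patients treated in Europe and North America, and each leads into the same description of disease status after radiotherapy and of the 42-day window. The SAP sentence is in effect the Section 4.1 sentence with a different number. The 150 therefore cannot be read as a count of patients screened or enrolled.

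What is at stake is whether the protocol states its own planned size correctly. A reader who relied on Section 4.1 alone would expect 48 more treated patients than the rest of the plan provides for, and a somewhat narrower confidence interval for the primary endpoint.

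**Working it through.** **Inputs**

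| Quantity | Value | Source |
|---|---|---|
| Treated | about 150 | Protocol 4.1 |
| Treated | about 102 | Protocol synopsis (two places), Protocol 9.2, SAP 1.2, SAP 1.3 |
| Standard cohort | about 59 | Protocol synopsis, Protocol 9.2, SAP 1.3 |
| Palliative cohort | about 43 | Protocol synopsis, Protocol 9.2, SAP 1.3 |
| Screened | about 148 | Protocol synopsis |
| Minimum for precision | 60 overall; 30 per cohort as illustration | Protocol 9.2, SAP 1.3 |

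**Step 1. Reproduce the plan's total.** 59 + 43 = 102. This agrees with the stated total wherever the split is given.

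**Step 2. Size of the gap.** 150 − 102 = 48 patients. 48 / 102 = 0.471, or 47%. Rounding, or the word approximately, does not cover a gap of that size.

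**Step 3. Compare with the screening number.** 102 / 148 = 68.9% of screened patients treated, which is possible. 150 / 148 = 101%, which is not: more patients would be treated than screened.

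**Step 4. Does any calculation use the 150?** Protocol Table 11 (SAP Table 1) gives exact 95% intervals. With x = p × n, the Clopper-Pearson limits are the 0.025 quantile of Beta(x, n − x + 1) and the 0.975 quantile of Beta(x + 1, n − x).

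- n = 60, p = 0.12, x = 7.2: 5.0% to 23.0% (±9.0). Matches the table.
- n = 30, p = 0.12, x = 3.6: 3.1% to 29.1% (±13.0). Matches the table.

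The printed precision is reproduced from 60 and 30 alone. Neither 102 nor 150 enters it.

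**Step 5. What the two totals would mean for the primary estimate, for illustration.** Same formula at 12%:

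- n = 102, x = 12.24: 6.4% to 19.9%, about ±6.8 points.
- n = 150, x = 18: 7.3% to 18.3%, about ±5.5 points.

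A reader who took 150 as the study size would expect a half-width about 1.3 points narrower (6.8 − 5.5) than 102 patients would give. The plan prints neither interval.

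**The case against.** The strongest case on the other side is that this is editorial. The safety analysis set is everyone who received at least one dose (Protocol 9.3.1, SAP 2.1.1), whatever number was planned. The primary data cut-off is set six months after the last patient's first dose (Protocol 9.5, SAP 5), not at a patient count. The precision argument needs only 60. The sections that govern the analysis all agree on 102. All of this stands, and it limits the point to document consistency. It does not remove the contradiction: no reading of Section 4.1 makes 150 treated patients compatible with 102 treated or with 148 screened.

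A second objection is that 102 should not be treated as settled merely because it appears more often. That also stands in part. The weight of the text is strongly for 102, and it is the only total with a cohort breakdown, but the sponsor should confirm it when reconciling the sections.

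On the cause, the version history suggests that Section 4.1 was missed when the sample size was updated. That is a plausible inference only. The contradiction is between current passages and stands without it.

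A reader might go further and infer that the trial falls 48 patients short of what its precision requires. The documents do not support that. The stated minimum is 60, which 102 exceeds, and the cohorts of 59 and 43 both exceed the 30 used in the per-cohort illustration.

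**Conclusion.** The point holds as an internal inconsistency in the stated study size. Protocol Section 4.1 is 48 patients (47%) above the total given in all other legible text, and above the number to be screened. It is worth correcting because the planned number treated is a basic design figure and is wrong on its face in the design section. It has no consequence for any analysis, precision figure or data cut-off.

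This rests on two conditions. First, 102 is taken as the intended number, subject to the sponsor's confirmation. Second, Figure 1 is not reproduced in the available text of either document, so the statement that everything else agrees covers legible text only.

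**What to change.** In Protocol Section 4.1, change the planned number treated from approximately 150 to approximately 102, after the sponsor has confirmed that 102 is intended. At the same time, check that Figure 1 in the protocol and Figure 1 in the SAP show the same total and the same cohort sizes.

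The cost is one figure in one sentence and a check of two diagrams. The synopsis, Section 9.2 and the SAP text need no edit if 102 is confirmed. Enrolment, the analysis set and the planned analyses are unaffected.
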